2.3 Hypotheses and Specific Aims

The trial will test two hypotheses:

Hypothesis-1: Grafting with Bone Allograft is an efficacious method of enhancing the development of new bone fill in extraction sockets.

Hypothesis-2: Bone Allograft/Amniotic allograft will aid osseous healing and will preserve alveolar ridge dimensions of extraction sockets more effectively than extraction sites grafted with Bone Allograft alone.

Specific Aims

- 1: Compare the efficacy of bone grafting with and without enrichment with amnion.
- 2: Compare alveolar ridge dimensions between groups after 7 weeks of post-extraction healing.
- 3: Compare soft tissue healing between groups at week-1, week-2, week-4 and after 7 weeks of post-extraction healing.

- 4: Assess quantitative bone fill between groups after 7 weeks of post-extraction healing
- 5: Compare qualitative bone fill between groups after 7 weeks of post-extraction healing.
- 6: Assess and compare the relationship of osseous healing and implant stability at insertion across groups after 8 weeks of post-extraction healing.
- 7: Compare implant stability between groups at 12 months and 24 months post-restoration.
- 8: Assess changes in longitudinal crestal bone level between groups at 12 and 24 months after permanent prosthetic attachment.

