4.2 Randomization

Participants will be stratified for smoking status and randomized to one of two extraction/grafting groups. In the case of multiple tooth sites within one participant, all the tooth sites will be assigned to receive the same graft material.

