4.9 Tissue Biopsy and Implant Placement

After reviewing the CBCT scans the investigator will determine whether or not the sockets have enough bone-fill to enable the surgical placement of implants. The diameter and length of the implants placed will be determined by the surgeon/investigator based on the tooth location, anatomy, and bone volume determined from the CT scan prior to placement. Immediately prior to implant placement, a tissue biopsy will be harvested from the center of one grafted site. Implants will be placed following standard procedures outlined in the Manual of Procedures.

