11.0 CRITERIA FOR SUCCESS

11.1 Grafts

The success criteria for this investigation are determined as follows: Grafts will be deemed successful if there are no reported symptoms or clinical signs of post-application allergy, toxic reactions or evidence of gross local or systemic infections.

Histological and histomorphometric analyses will provide evidence of the relative success or failure of graft materials to enhance formation of new osseous tissue in extraction sockets. Results will be compared and between experimental groups.

A site that fails to meet the stated criteria for success, or where the width of the ridge remains too narrow for implant insertion will be re-grafted (an offer that patients may decline). The site may receive an implant at a later date but the site will be exited from the study results.

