13.3 Outcome Endpoints

The primary efficacy parameter for implant success will be the duration of implant survival from surgical placement to 24 months post-placement across all groups. Measurement of bone height along the implant mesial and distal surfaces at 12 and 24-month follow-up evaluations will be captured from radiographic images and compared to same measurements at insertion. These measurements will be used to derive changes from baseline values.

Efficacy endpoints will include implant and prosthesis function as assessed by gingival health, bone levels and participant subjective satisfaction with the study therapy. Differences between groups will

be calculated and used to determine if osseous changes and implant function are different between groups.

Safety will be evaluated by clinical signs and symptoms of dental and medical events.

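### Implant survival is timed from placement and unimplantable sites leave the results, so any between-arm implant comparison is made in a set selected by graft outcome

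*Combined protocol and SAP*

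**What the plan says.** Section 4.2 sets the point of randomisation: "Participants will be stratified for smoking status and randomized to one of two extraction/grafting groups". Table 2 puts randomisation at V-1, grafting at V-2 and implant placement at V-7 (week 8).

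Between grafting and placement there is a decision. Under section 4.9, once the CBCT scans have been reviewed, "the investigator will determine whether or not the sockets have enough bone-fill to enable the surgical placement of implants". Section 11.1 adds that a site failing the graft success criteria, or one "where the width of the ridge remains too narrow for implant insertion will be re-grafted", unless the patient declines. It continues: "The site may receive an implant at a later date but the site will be exited from the study results".

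The implant endpoint starts after that decision. Section 13.3: "The primary efficacy parameter for implant success will be the duration of implant survival from surgical placement to 24 months post-placement across all groups". The same section says that differences between groups will "be calculated and used to determine if osseous changes and implant function are different between groups". Section 2.1 also gives comparison of the implant reconstruction as a purpose of the study.

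Hypothesis-2 in section 2.3 expects that the combined graft "will preserve alveolar ridge dimensions of extraction sockets more effectively than extraction sites grafted with Bone Allograft alone".

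The analysis plan in section 13.4 names no analysis population, no rule for participants or sites without an implant, and no survival method.

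**The concern.** The randomised treatment is the graft, but the clock for the implant parameter starts only if the graft result permits an implant. A socket that does not reach placement has no survival time, so it is neither an event nor a censored observation. Section 11.1 turns this into an explicit exclusion and extends it to sites that are re-grafted and implanted later.

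Bone fill and ridge width decide who enters the implant set, and these are the features the test graft is meant to improve. If the arms differ in how many sockets become implantable, the two sets of placed implants are no longer comparable by randomisation. A graft that often leaves a socket unusable could then show the same implant survival as one that never does.

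**Working it through.** The plan states no power, event rate, graft-failure rate or dropout rate, so it has no figure of its own to reproduce. The check is first a reading of the sections together, then illustrations on assumed rates.

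**Order of events**

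1. Randomisation to graft: V-1 (section 4.2, Table 2).
2. Grafting: V-2.
3. CBCT and decision on implantability: weeks 7 to 8 (sections 4.8 and 4.9).
4. Sites failing the graft criteria or too narrow: removed from the results (section 11.1).
5. Survival clock starts: implant placement, V-7 (section 13.3).

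Steps 3 and 4 follow randomisation and come before the clock starts. A socket held back for bone fill alone is not named in section 11.1, but it still has no survival time while it has no implant.

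**Inputs for the illustrations**

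- From the documents: 20 participants, 10 per group (section 3.1).
- Assumed: one site per participant, and every no-implant and survival rate below. Section 4.1 allows up to four sites. A participant with several sites loses the outcome entirely only if all of them are excluded; otherwise the selection is within the participant.

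**How likely is at least one exclusion?** P = 1 − (1 − p)^20, where p is the no-implant rate.

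- p = 2%: 1 − 0.98^20 = 33%
- p = 5%: 1 − 0.95^20 = 64%
- p = 10%: 1 − 0.90^20 = 88%

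Each participant lost is 1/10 = 10% of an arm.

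**What can the two counts show?**

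- *Difference hidden.* Three control sockets and no test socket are unimplantable, and no placed implant fails. Among placed implants: 7/7 v 10/10, or 100% v 100%. Among all grafted: 7/10 v 10/10, or 70% v 100% (Fisher p = 0.21).
- *Direction reversed.* As above, but one test implant fails. Among placed implants: 7/7 v 9/10, or 100% v 90%, favouring control (p = 1.00). Among all grafted: 7/10 v 9/10, or 70% v 90%, favouring test (p = 0.58).

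**In expectation.** Success among all grafted = P(implanted) × P(survival given implanted). Take survival once implanted as 95% in both arms, so the placed-only difference is always 0.

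- No implant in 30% of control and 10% of test: 0.90 × 0.95 − 0.70 × 0.95 = 0.855 − 0.665 = +19 points for test.
- No implant in 10% of each: 0.855 − 0.855 = 0.
- No implant in 10% of control and 30% of test: 0.665 − 0.855 = −19 points.

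The distortion can therefore be zero, or can run either way, depending on rates the documents do not give.

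**The case against.** The strongest reply is that section 13.3 calls survival primary for implant success, not for the trial as a whole. The second objective, in section 2.2, concerns implants after placement, for which placement is the natural time origin, and the synopsis null hypothesis is about healing after extraction. This stands in part. A reader might infer that placement-based survival is the trial's sole primary outcome. No other parameter is called primary, but the text does not go that far.

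The plan also never specifies a between-arm survival test. The phrase about all groups could mean a pooled figure, and section 13.4 has no survival method. However, sections 2.1 and 13.3 do promise a between-group comparison of implant results, and a pooled figure would still omit graft failures.

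A reader might also infer that the trial cannot see a failed graft at all. The documents do not support that. The week-7 CBCT measures bone fill and ridge dimensions before the placement decision, under aims 2, 4 and 5. Those outcomes do not have the time-origin problem, although the exit rule in section 11.1 could be applied to them as well.

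Finally, every magnitude above is assumed, and with 10 per arm none of the illustrated contrasts reaches significance on either count. That is correct. The point concerns which quantity is estimated, not whether a test would be significant.

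**Conclusion.** The point holds conditionally. If at least one site is excluded under sections 4.9 or 11.1, a between-arm comparison of implant survival or function is made in a set selected by graft outcome and loses the protection of randomisation. If no site is excluded, nothing is lost.

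The size and direction of the bias are unknown. On assumed rates the placed-only difference can be 0 when the all-grafted difference is 19 points either way, and it is undistorted when the arms have equal no-implant rates and equal survival once implanted. A reader might infer that the rule must work against the better graft, because that graft brings more marginal sockets into its own survival set. The documents do not establish this.

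The time-origin problem is confined to the implant parameter. The wording should be changed before analysis, because the exclusion is a written rule that Hypothesis-2 itself expects to act unequally on the arms.

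**What to change.** **Sections 13.3 and 13.4.** Make the between-arm implant comparison on all randomised participants, timed from grafting (V-2) to a stated end of follow-up. The end needs stating because section 13.3 counts 24 months from placement and section 8.0 counts 24 months from restoration. Suggested wording: *Time from grafting to implant failure. A study socket with no implant placed at the planned implant visit under the criteria of sections 4.9 and 11.1 counts as a failure at that visit.*

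**Reason for non-placement.** Record it on the CRF against those criteria. Only laboratory technicians are stated to be blinded (section 6.3), so a free judgement of cause should not decide between failure and censoring. Censor only documented reasons unrelated to the graft, such as withdrawal, and add a sensitivity analysis that counts all non-placement as failure.

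**Unit of analysis.** Analyse by participant, stating how several sockets are combined, or by site with clustering by participant.

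**Section 11.1.** Amend the exit sentence so that these sites stay in the analysis as failures; otherwise it contradicts the new wording in 13.3. Clinical management, including the placement decision and the re-grafting offer, is unchanged.

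**Reporting.** Keep survival from placement as a supporting result, and tabulate the numbers grafted, implanted and surviving by arm.

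**Cost.** Text changes in three sections, one table, one sensitivity analysis, and one CRF item if the reason is not already captured. Stated survival percentages will be lower than placement-based figures wherever a socket is not implanted.

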6.6 Implants Exposed

Implants will be exposed upon the investigator's determination that the implants are sufficiently integrated to withstand the forces of loading. In general, mandibular implants will be uncovered and restoration initiated approximately 4 months after placement; maxillary implants will be uncovered and restoration initiated approximately 6 months after placement.

Prior to exposing the implants subjects will be given a loading dose of antibiotics based on their medical history and concomitant medications. Local anesthesia will be achieved in the region by regional block or local infiltration. Conscious sedation may be added at the surgeon's discretion to help manage a patient's anxiety. The facial area will be scrubbed by 2% Chlorhexidine soap and the oral cavity disinfected by rinsing for 1 minute with a 0.12% chlorhexidine gluconate antimicrobial oral rinse prior to the procedure.

Once the treatment areas are sufficiently anesthetized a crestal incision will be made to reveal the top of the implant and an abutment will be attached. The incision will be closed with sutures and the temporary prostheses will be adjusted. Clinical photographs will be taken before, during and after the procedure; following the procedure and standardized intra-oral radiographic images of each implant site will be captured.

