7.0 PERMANENT RESTORATION OF IMPLANTS

Implant restoration will be completed according to the prosthetic guidelines. Each implant will be restored in the conventional manner with an aesthetically pleasing single crown restoration. The restoring dentist will select restoring materials based on his discretion and the individual patient needs. Prosthetic restoration of the implants will require numerous visits to the restorative dentist over a

period of one to two months. The restoring dentist will advise when additional visits are necessary. Photographs and radiographs will be taken of each area when the final restoration is cemented.

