8.0 LONGITUDINAL FOLLOW-UP

Post-Restoration Follow-up Evaluations (12-months and 24-months after the implant is restored)

Participants will return to the clinic at 12 and 24 months following permanent implant restoration. Evaluation of implant function and surrounding tissue health will be determined based on an interview with the participant, clinical examination of the study sites and an analysis of radiographic and photographic data.

At each visit, study personnel will review and update the participant's health history and record any adverse experiences; a study dentist will complete a thorough periodontal evaluation of the implant area and provide an assessment of the prosthetic attachment interface. A set of standardized periapical radiographs and clinical photographs will be made.

Case report forms will be used to record the following observations for each implant site:

- Overall soft tissue health
- Plaque and gingivitis scores (modified Löe and Sillness)
- Pocket depth and clinical attachment level
- Implant Stability
- Retention and stability of prosthetic attachment
- Overall aesthetics (soft tissue contours)
- Assessment of reported pain
- Implant survival

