9.0 RADIOGRAPHIC AND PHOTOGRAPHIC SURVEYS

9.1 Intra-oral Radiographic Images

Standardized intra-oral periapical digital radiographic images will be obtained of each site prior to implant placement, when the implants are placed, when the implant is exposed, at permanent implant restoration and at twelve and twenty-four months after the implants are restored. A minimum of six images per study site over the duration of the study will be obtained. Additional images may be obtained based on the study dentist's determination of need.

Radiographic images will be used to monitor osseous health at the bone-implant interface, to verify implant position, to assess the quality of implant-attachment interface and to capture measurements of longitudinal osseous support to the implants. Consistently careful technique will yield images with similar geometry and with constant density leading to a valid and dependable analysis.

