13.1 Objective Data

Bone biopsies preserved in the trephines and stored in formalin will be submitted to UAB's CMBD Core Laboratory. Trephine core 2x6 mm will be stained with hematoxylin and eosin and processed for histologic and histomorphometric analysis. Amount of bone fill and remaining bone graft (% of new bone fill, % of residual graft and % of soft tissue) material will be determined and compared across groups. Torque measurements will be recorded for each site at implant placement.

Cone Beam Computed Technology (CBCT) will be used to capture quantitative natural bone fill and bone fill following grafting applications at each extraction site.

Image analysis software will be used to capture images from the standardized radiographs taken at 12 and 24 months following implant placement. Analysis procedures will assess the implant/bone interface and measure changes in adjacent crestal alveolar bone levels over time.

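### Crestal bone change is derived only from the insertion film, so it cannot separate remodelling before restoration from change after it, and the plan counts 12 and 24 months from two different dates

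*Combined protocol and SAP*

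**What the plan says.** Section 13.3 describes mesial and distal bone height read from radiographs at the 12- and 24-month evaluations and "compared to same measurements at insertion". It adds: "These measurements will be used to derive changes from baseline values". Insertion is the only reference it names.

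Aim 8 in section 2.3 is to "Assess changes in longitudinal crestal bone level between groups at 12 and 24 months after permanent prosthetic attachment". Section 8.0 agrees on the date from which the visits run: "Participants will return to the clinic at 12 and 24 months following permanent implant restoration". Section 3.2 and the synopsis do the same, and section 9.1 schedules films "at permanent implant restoration and at twelve and twenty-four months after the implants are restored".

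Other places use a different starting date. Section 13.1 analyses "standardized radiographs taken at 12 and 24 months following implant placement". Section 13.0 also counts from placement, section 12.2 counts the final visit from insertion, and the survival parameter in 13.3 runs to 24 months after placement.

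The time from insertion to restoration is not fixed. Section 6.6 gives about 4 months to exposure in the mandible and about 6 in the maxilla, subject to judgement: "Implants will be exposed upon the investigator's determination that the implants are sufficiently integrated to withstand the forces of loading". Section 7.0 then allows a "period of one to two months" for the restorative visits, and section 3.2 leaves their scheduling to the restoring dentist.

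**The concern.** A bone-level change that starts at insertion adds together two periods. The first runs from insertion to the crown, in a socket grafted 8 weeks before insertion. The second runs from the crown to the follow-up visit. Aim 8 dates its assessments from the crown, but the only planned score includes the first period as well.

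If the groups differ on that score, the reader cannot say whether the graft affected early settling of the crest, stability after restoration, or both. If they do not differ, opposite effects in the two periods could be hidden. The first period also differs in length between jaws and with clinical judgement, and randomisation is stratified by smoking status only (section 4.2), so arms of 10 may differ in jaw mix by chance.

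The two starting dates add a second problem: as written, the length of the window being analysed depends on which section is followed.

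**Working it through.** **The plan's own figure.** Section 9.1 states a minimum of six films per site. Its list is: before placement, at placement, at exposure, at restoration, at 12 months, at 24 months. That is 6, so the figure reproduces, and the restoration film is one of the six. Sections 4.11 and 7.0 and Table 3 (V-10) also require it. The plan gives no SD, effect size or power calculation for crestal bone change.

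**Inputs.** Placement to exposure: 4 months (mandible) or 6 months (maxilla), section 6.6. Exposure to restoration: 1 to 2 months, section 7.0. All are approximate.

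**Insertion to restoration** = time to exposure + restorative period.
- Mandible: 4 + 1 to 4 + 2 = 5 to 6 months.
- Maxilla: 6 + 1 to 6 + 2 = 7 to 8 months.

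**Visits counted from restoration** (Aim 8; sections 3.2, 8.0, 9.1). Window = insertion-to-restoration time + 12 or 24. Share before restoration = insertion-to-restoration time / window.
- 12-month visit: mandible 17 to 18 months, maxilla 19 to 20. Share from 5/17 = 29% to 8/20 = 40%.
- 24-month visit: mandible 29 to 30 months, maxilla 31 to 32. Share from 5/29 = 17% to 8/32 = 25%.

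**Visits counted from placement** (sections 12.2, 13.0, 13.1; survival in 13.3). The window is 12 or 24 months for every implant.
- 12 months: share from 5/12 = 42% to 8/12 = 67%, leaving 4 to 7 months after restoration.
- 24 months: share from 5/24 = 21% to 8/24 = 33%, leaving 16 to 19 months after restoration.

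**Sensitivity.** Adding the 14-day visit after exposure (section 6.7) as a further half month gives 5.5 to 8.5 months before restoration. Clinical discretion could move individual implants outside either range.

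**Chance imbalance by jaw.** Assume one site per patient and a mandibular share of 20% to 50%; neither is given in the documents. With independent binomial counts in two arms of 10, the probability that the arms differ by 3 or more mandibular patients is 16% to 26%. The jaws differ by 2 months, so a difference of 3 in 10 shifts the mean pre-restoration interval by 0.3 × 2 = 0.6 month. That is about 3% to 4% of a 17-20 month window (0.6/20 to 0.6/17), a small shift.

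**The case against.** The strongest case for the plan is that insertion is a proper baseline. The second objective in section 2.2 concerns implant stability from placement onwards, which an insertion film fits. Aim 8 says when bone level is assessed but names no baseline and does not limit itself to loss in function. Change from insertion is a legitimate total, and randomisation protects the group comparison in expectation. All of this stands.

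A restoration baseline also has its own cost. Restoration follows a judgement that the implant has integrated, so the later contrast conditions on a later post-randomisation event. It leaves out implants lost before restoration and removes any graft effect on the crest during healing. Insertion is itself about 8 weeks after grafting, and sites that fail the graft criteria have already left the study results (section 11.1), but restoration conditions further. This is why total change should be kept, not replaced.

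Section 9.1 does say that the serial films serve to measure osseous support over time, so reading the restoration film is within the plan's general intent. What is missing is a defined contrast that uses it; 13.3 defines only the one from insertion.

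A reader might infer that the current endpoint is biased, perhaps because the graft delays exposure. The documents do not support that. They make such a dependence possible, since exposure rests on judged integration and Hypothesis-2 expects better osseous healing with amnion, but nothing shows that it occurs or in which direction.

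**Conclusion.** The point holds as a limit on interpretation and as an inconsistency in dates. On the restoration clock, about 29-40% of the 12-month window and 17-25% of the 24-month window precedes restoration. On the placement clock the total windows are equal, but the shares rise to 42-67% and 21-33%. Under either clock, one change score from insertion cannot separate healing-phase remodelling from change after restoration.

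These are shares of elapsed time, not of bone lost. They rest on the protocol's approximate timings, and without an SD or a rate of bone loss no effect in millimetres or on power can be computed. A reader might also infer that insertion is the wrong baseline and must be replaced for Aim 8. The documents do not support this, because Aim 8 names no baseline and the section 2.2 objective starts at placement. The change is a cheap improvement, not the repair of an invalid comparison.

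**What to change.** 1. Reconcile the starting date for 12 and 24 months: sections 12.2, 13.0, 13.1 and 13.3 must agree with Aim 8 and sections 8.0 and 9.1. If survival is meant to run from placement while bone level is dated from restoration, say so explicitly.
2. In 13.1 and 13.3, add mesial and distal bone-level readings on the restoration (V-10) film.
3. Keep change from insertion as the total-change measure. For Aim 8, add two separately reported intervals: insertion to restoration, with elapsed months by group and jaw; and restoration to the 12- and 24-month evaluations.
4. State that the post-restoration interval includes only implants that reach restoration, and report by group the implants lost before it.

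The cost is one extra reading per site on a film already acquired, with no added visit or exposure, plus wording in the sections named. The downsides are more interval outcomes to report and a post-restoration contrast that is conditional on reaching restoration.
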